Since this amendment recruitment continued to be difficult, and a new substantial amendment in January 2022 has formally closed the second cohort, due the effect of ongoing COVID-19 pandemic as well as associated clinical factors.

Following the closure of the second cohort, the first cohort sample size is now expanded to a range of 31-67 patients with recruitment to complete at the end of December 2022. The precise statistical implications of the eventual recruitment total are detailed in full within section 3.

2. Study Objectives and Hypotheses

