0.80	4 months OS	6 months	83
0.80	4 months	7 months	45
0.90	4 months	6 months	122
0.90	4 months	7 months	67

The study will therefore aim to recruit between 31 and 67 patients to Cohort 1 within the allotted study period. This sample size range is estimated to have a power of 80% to 90% in determining the PFS and/or the OS of the study cohort.

As for DCR, the minimum range of this sample size (i.e. 31) would require ≥ 10 DCR to recommend Pembrolizumab for further evaluation, assuming an unacceptable DCR of $\leq 20\%$ (P0) vs the desired rate of $\geq 40\%$ (P1). This Fleming single-stage design would provide a one-sided alpha of 8% and a power of 86%. Different simulations for the minimum DCR needed ($H_0: P \leq 0.2$ vs $H_1: P \geq 0.4$) given a one-sided alpha $\leq 10\%$ and power $\geq 80\%$ are presented below:

Power	N	Alpha	Minimum DCR needed
0.80	35	0.03	12
0.86	31	0.08	10
0.90	47	0.04	15
0.91	42	0.06	13
0.91	36	0.09	11

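### The DCR pass marks in SAP 3.5 follow no single alpha: 11 of 35 fails while the weaker 11 of 36 passes, and no mark is listed above N=47 although N may reach 67

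*SAP*

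**What the plan says.** SAP 3.5 sets a null disease control rate (DCR) of at most 20% against a desired rate of at least 40%. For 31 patients it requires 10 or more with disease control before pembrolizumab is recommended for further evaluation, and adds: "This Fleming single-stage design would provide a one-sided alpha of 8% and a power of 86"%.

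A table follows, introduced as "Different simulations for the minimum DCR needed", under the common condition of one-sided alpha at most 10% and power at least 80%. Its columns are power, N, alpha and minimum count. Three of its five rows are "0.86 31 0.08 10", "0.80 35 0.03 12" and "0.91 36 0.09 11". The other two are N=42 (need 13, alpha 0.06, power 0.91) and N=47 (need 15, alpha 0.04, power 0.90).

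The SAP Introduction says "the first cohort sample size is now expanded to a range of 31-67 patients with recruitment to complete at the end of December 2022". The protocol's Trial Summary and section 1.3.1 end recruitment at 67 patients or at the end of December 2022, whichever is sooner.

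SAP section 6 states that the primary outcome is tested two-tailed at 5%, and SAP 5.1 lists DCR under the primary efficacy endpoint.

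**The concern.** A go/no-go count should have one property above all: stronger evidence should not fail where weaker evidence passes. The rows for N=35 and N=36 break this. With 11 controlled patients out of 35 the mark is missed. Add one patient without disease control and it is met.

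The second problem is coverage. The final N is whatever recruitment yields between 31 and 67, yet marks are given for five values and none for 48 to 67, which includes the target of 67. The stated condition does not fill the gap, because it usually allows several marks. In an open-label trial the mark could then be settled after the count is known, and the recommendation would turn on that choice.

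**Working it through.** **Inputs (SAP 3.5).** P0=0.20, P1=0.40; limits: one-sided alpha ≤0.10, power ≥0.80; the five listed pairs of N and mark r; planned N from 31 to 67.

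**Formulas.** With X binomial(N, p): alpha = P(X≥r | N, 0.20) and power = P(X≥r | N, 0.40).

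**Step 1. Reproduce the SAP's rows.**

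| N | Mark | SAP alpha / power | Exact alpha / power |
|---|---|---|---|
| 31 | 10 | 0.08 / 0.86 | 0.0746 / 0.8566 |
| 35 | 12 | 0.03 / 0.80 | 0.0344 / 0.8048 |
| 36 | 11 | 0.09 / 0.91 | 0.0889 / 0.9096 |
| 42 | 13 | 0.06 / 0.91 | 0.0621 / 0.9140 |
| 47 | 15 | 0.04 / 0.90 | 0.0366 / 0.9012 |

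Four rows match at two decimals. At N=31 the power matches, but the alpha is 7.46%, which rounds to 7%, not 8%.

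**Step 2. The reversal.** 11/35 = 31.4%, with P(X≥11 | 35, 0.20) = 0.0747: below the mark of 12. 11/36 = 30.6%, with P(X≥11 | 36, 0.20) = 0.0889: meets the mark of 11. The probability of exactly 11 of 35 is the difference between the tails at 11 and 12:
- true DCR 20%: 0.0747 − 0.0344 = 0.0403, or 4.0%;
- true DCR 40%: 0.8877 − 0.8048 = 0.0829, or 8.3%.

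**Step 3. Is this only binomial discreteness?** No. For a fixed r, P(X≥r | N, 0.20) rises with N, because another patient can only add to the count. So the smallest r that meets a given cap can stay level or rise with N, but not fall. Direct calculation for N=31 to 67 confirms this at caps of 10% and 5%. At 10% the mark is 11 at both N=35 and N=36; at 5% it is 12 at both. The listed drop arises because N=35 is set near 3% and N=36 near 9%.

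**Step 4. How many marks does the stated condition admit?**

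| N | Marks with alpha ≤0.10 and power ≥0.80 | Exact alpha, lowest to highest mark |
|---|---|---|
| 31 | 10 | 0.0746 |
| 35 | 11, 12 | 0.0747, 0.0344 |
| 36 | 11, 12 | 0.0889, 0.0424 |
| 42 | 13, 14 | 0.0621, 0.0298 |
| 47 | 14, 15, 16 | 0.0721, 0.0366, 0.0171 |
| 67 | 19, 20, 21, 22, 23 | 0.0639, 0.0357, 0.0188, 0.0093, 0.0043 |

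Over all 37 values, exactly one mark qualifies at N=31, 32, 33, 34 and 37. Two or more qualify at the other 32 (35, 36 and 38 to 67).

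**Step 5. What a late choice can do.** At N=67, any count from 19 to 22 passes under the lowest admissible mark and fails under the highest. Its probability is 0.0639 − 0.0043 = 0.0596 at a true DCR of 20%, and 0.9825 − 0.8586 = 0.1239 at 40%. Alpha stays within the limit: even the most lenient mark, 19, has alpha 6.4%.

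**The case against.** The strongest reply is that the table was never meant as a set of decision rules. It is introduced as simulations, its rows run in order of power rather than N, and the recommendation wording is attached to N=31 alone. Three rows look like answers to conventional design targets: N=35 with 12 is the smallest N for 5% alpha and 80% power, N=47 with 15 for 5% and 90%, and N=36 with 11 for 10% and 90%. The SAP does not say this, but if it is right, the drop from 12 to 11 reflects different targets and is not a slip. A reader might infer that the whole table decides the recommendation; the text does not go that far. What remains is that the column is headed as the minimum needed, no row or selection rule is named as binding, and no other DCR rule appears. SAP 6.3 only calculates the proportion.

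A reader might also infer that alphas from 3% to 9% are an error in themselves. They are not. Attained alpha must vary with a binomial count, and under a fixed 10% cap it still runs from 5.1% to 9.95%. Nor is the type I error uncontrolled: every admissible mark has alpha at most 10% by definition, and recruitment stops on a number or a date, not on DCR.

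The weight of the point is limited too. The protocol calls the trial hypothesis-generating, SAP 3.5 recalculated the sample size for PFS and OS, protocol 8.2 has no DCR threshold, and SAP 6.3 names response rate as the variable that governs accrual.

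**Conclusion.** The point holds as a defect in specification: SAP 3.5 offers pass marks that are not coherent as a set and do not cover the planned range of N. The listed marks reverse the order of evidence between N=35 and N=36. There is no mark for 32 of the 37 possible sample sizes (32–34, 37–41, 43–46 and 48–67). The stated limits leave a choice of marks at 32 of the 37 as well, though not the same 32.

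The consequence is a verdict that can depend on a choice made after the count is known. It is not an alpha above the SAP's 10%. Apart from the N=31 alpha, the printed error rates are correct.

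This rests on exact binomial tails, on the SAP's 20% and 40%, on a single look at the final N, and on N not being steered by DCR results. It is a should-fix, given the trial's hypothesis-generating purpose and its sizing on PFS and OS.

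**What to change.** Before DCR is tallied, amend SAP 3.5 as follows.

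1. State that the DCR rule is binding.
2. Fix one one-sided alpha cap and reconcile it with the two-tailed 5% test in SAP section 6. That test implies 2.5% in the upper tail, which no listed mark meets (lowest exact alpha 3.4%).
3. State which population's N selects the mark. SAP section 4 makes intention-to-treat the default, but the 20-patient rule in SAP 3.5 and the per-protocol set use assessable patients.
4. Replace the five rows with the smallest count meeting the cap at every N from 31 to 67. With the SAP's own 10% cap:

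| N | 31–32 | 33–36 | 37–40 | 41–45 | 46–49 | 50–53 | 54–57 | 58–62 | 63–66 | 67 |
|---|---|---|---|---|---|---|---|---|---|---|
| Mark | 10 | 11 | 12 | 13 | 14 | 15 | 16 | 17 | 18 | 19 |

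Exact alpha is then 5.1% to 9.95% and power at least 83% throughout.

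5. Correct the N=31 alpha from 8% to 7.5%.

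The cost is one table and a few sentences. With the 10% cap, the marks at N=31, 36 and 42 stand, but those at N=35 and N=47 fall by one. Their alphas rise from 3.4% to 7.5% and from 3.7% to 7.2%. Since the trial is open-label and responses are already documented, that choice should be justified and dated.

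A 5% one-sided cap is an alternative: 11 at N=31, 12 at N=35 and 36, 15 at N=47, 20 at N=67. Power then falls below 80% at N=31 to 34 and at N=37 (75.5% at N=31), and this must be stated. At 2.5% the mark at N=31 would be 12, with power 62%.

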3.6 Schedule of Time and Events

Table 3 summarizes the trial procedures to be performed at each visit. Individual trial procedures are described in detail below. Treatment is divided into cycles of 21 days, with visits and assessments specified according to the relevant cycle.

Unless otherwise indicated, scheduled assessments may take place within ± 3 days of the specified visit. Assessment days are relative to the start of study treatment i.e. Cycle 1 Day 1.

If a patient has a treatment break, please contact the Clinical Trials Section (CTS) for advice regarding the timing of research blood assessments. All other assessments, including laboratory safety assessments, vital signs and radiological imaging should continue to be performed.

Furthermore, additional evaluations/testing may be deemed necessary by the Sponsor and/or MSD for reasons related to subject safety. In some cases, such evaluation/testing may be potentially sensitive in nature (e.g., HIV, Hepatitis C, etc.), and thus local regulations may require that additional informed consent be obtained from the subject. In these cases, such evaluations/testing will be performed in accordance with those regulations.

During the COVID-19 pandemic, patients whom are under ongoing treatment can be offered longer intervals of 1 to 2 weeks between treatment to avoid peak COVID-19 capacity issues.

Table 2: Schedule of Assessments

Trial Period:	Screening Phase	Treatment Cycles								End of Treatment	Post-Treatment		
Treatment Cycle/Title:	Study Screening	1	2	3	4	5	6	7	8	Discon	Safety Follow-up	Follow Up Visits	Survival Follow-Up
Scheduling Window (Days):	-28 to -1		± 3	± 3	± 3	± 3	± 3	± 3	± 3	At time of Discon	30 days post discon	Every 8 weeks post discon	Every 12 weeks
Administrative Procedures													
Pre-screening Visit													
Informed Consent	X												
Inclusion/Exclusion Criteria	X												
Demographics and Medical History	X												
Prior and Concomitant Medication Review	X	X	X	X	X	X	X	X	X	X	X		
Trial Treatment Administration		X	X	X	X	X	X	X	X				
Trial Treatment Compliance		X	X	X	X	X	X	X	X				
Quality of Life Questionnaire (EORTC QLQ-C30)	X					X				X			
Post-study anticancer therapy status											X	X	X
Survival Status		X	X	X	X	X	X	X	X	X	X	X	X
Clinical Procedures/Assessments													
Review Adverse Events	X	X	X	X	X	X	X	X	X	X	X		
Full Physical Examination	X ^a	X			X				X	X	X		
Directed Physical Examination	X ^a	X	X	X	X	X	X	X	X	X	X	X	
Vital Signs and Weight	X ^a	X	X	X	X	X	X	X	X	X	X	X	
ECOG Performance Status	X ^a	X	X	X	X	X	X	X	X	X	X	X	
Laboratory Procedures/Assessments: analysis performed by LOCAL laboratory													

Trial Period:	Screening Phase	Treatment Cycles								End of Treatment	Post-Treatment		
		1	2	3	4	5	6	7	8		Safety Follow-up	Follow Up Visits	Survival Follow-Up
Treatment Cycle/Title:	Study Screening												
Scheduling Window (Days):	-28 to -1		± 3	± 3	± 3	± 3	± 3	± 3	± 3	At time of Discon	30 days post discon	Every 8 weeks post discon	Every 12 weeks
Pregnancy Test –Serum β-HCG	X ^b		X ^c		X ^c		X ^c		X ^c				
PT/INR and aPTT	X ^d	X ^e	X ^e	X ^e	X ^e	X ^e	X ^e	X ^e	X ^e	X	X	X	
CBC with Differential	X ^d	X ^e	X ^e	X ^e	X ^e	X ^e	X ^e	X ^e	X ^e	X	X	X	
Comprehensive Serum Chemistry Panel including full or directed tumor marker panel (+/- NET serum markers)	X ^d	X ^e	X ^e	X ^e	X ^e	X ^e	X ^e	X ^e	X ^e	X	X		
Urinalysis	X ^d	X ^e	X ^e	X ^e	X ^e	X ^e	X ^e	X ^e	X ^e	X	X		
T3, FT4 and TSH	X ^d	X ^e	X ^e	X ^e	X ^e	X ^e	X ^e	X ^e	X ^e	X	X	X	
Efficacy Measurements													
Tumor Imaging	X ^f					X ^g			X	X (if not done within 12 weeks prior)		X	
Tumor Biopsies/Archival Tissue Collection/Correlative Studies Blood													
Archival or Newly Obtained Tissue Collection	X ^h												
Correlative Studies Blood & Urine Collection	X		X		X		X		X	X	X		

Trial Period:	Screening Phase	Treatment Cycles								End of Treatment	Post-Treatment		
Treatment Cycle/Title:	Study Screening	1	2	3	4	To be repeated beyond 8 cycles				Safety Follow-up	Follow Up Visits	Survival Follow-Up	
Scheduling Window (Days):	-28 to -1		± 3	± 3	± 3	± 3	± 3	± 3	± 3	Discon	Every 8 weeks post discon	Every 12 weeks	
aIn circumstances where screening assessments are conducted within 3 days prior to treatment initiation these can be used to cover both screening and C1D1.													
bMandatory negative blood serum pregnancy test at screening for patients of childbearing potential.													
cIn patients of childbearing potential: 
Mandatory negative serum pregnancy test within 72 hours prior to receiving study treatmentMandatory negative urine pregnancy test result available prior to receiving study treatment													
d Lab tests (blood samples for haematology, clinical chemistry and urinalysis) for screening should be performed within 10 days prior to the first dose of treatment. In circumstances where blood samples for haematology and clinical chemistry and urinalysis fulfils both the timeline of day -10 to 0 and 72 hours prior to C1D1 dosing these can be used for both screening and C1D1.													
eOn dosing days for all cycles, samples must be taken pre-dose (up to 72 hours prior to dosing).													
f Baseline assessment should be performed no more than 28 days before the start of study treatment and ideally as close as possible to the start of the study treatment.													
gSubsequent tumour assessments will be conducted every 12 weeks, with window for each assessment is ± 7 days.													
hTumour blocks / slides should be made available within 60 days of patient enrolment.													

4 Population of Analysis Sets

Unless otherwise stated, all analyses will be performed using the Intention-to-Treat (ITT) population which includes all study participants taking part in the trial regardless of whether they dropped out, fully adhered to the treatment or switched to an alternative treatment. A Per-Protocol (PP) population is additionally defined for the purpose of ad hoc or exploratory analyses.

4.1 Intention-to-Treat (ITT) Population

The Intention-to-treat population includes all enrolled patients eligible for the study.

4.2 Safety Population

The Safety Population is defined as all patients who received at least one dose of Pembrolizumab.

4.3 Per-Protocol (PP) Population

The Per-Protocol Population includes enrolled patients who are assessable for the primary endpoint. Assessable patients are those that have received at least 2 cycles of Pembrolizumab and are assessable for toxicity.

5 Variables of Analysis

5.1 Primary Efficacy Endpoint

The overall response to treatment is assessed using RECIST v1.1 and immune-related (irRECIST). Appendices A and B in the protocol present the guidelines for evaluation of objective tumour response Using RECIST 1.1 (Response Evaluation Criteria in Solid Tumours) or immune-related RECIST. The disease control rate will be calculated.

Disease Control Rate (DCR) - is defined as the proportion of patients in whom the best overall response is determined as complete response (CR), partial response (PR) or stable disease (SD) for at least 12 weeks in either RECIST or irRECIST criteria.

Overall Survival (OS) - defined as the length of time from study enrolment until death, withdrawal of consent, last follow-up date if lost to follow-up or the end of the study, whichever occurs first.

Progression Free Survival (PFS) – is defined as the length of time from study enrolment to first evidence of progressive disease identified at follow-up or confirmed disease progression at the end of the trial or death. Patients will be censored at the last follow-up date if they are lost to follow-up, withdrawn from the study or have not progressed at the end of study. Median PFS and its 95% confidence interval will be reported. Kaplan-Meier survival curves will also be plotted.

Quality of Life (QOL) is measured as scores from the EORTC QLQ-C30 version 3 questionnaire which will be administered at baseline, after 3 months and then at discontinuation of study treatment.

5.2 Secondary Efficacy Endpoints

- The incidence of adverse events up to 8 weeks after the last dose of Pembrolizumab will be noted.
- Incidence of adverse events up to 8 weeks after the last dose of Pembrolizumab in Performance Status 2 (PS2) patients.

5.3 Safety variables

Adverse Event (AE) - is any untoward medical occurrence in a patient or clinical trial subject administered a medicinal product and which does not necessarily have a causal relationship with this treatment. An AE can therefore be any unfavourable and unintended sign (including an abnormal laboratory finding), symptom, or disease temporally associated with the use of the trial medication, whether or not considered related to the IMP. Any worsening (i.e., any clinically significant adverse change in frequency and/or intensity) of a pre-existing condition that is temporally associated with the study treatment, is also an adverse event.

Details to be collected in the eCRF for each AE will include:

- AE description
- Date of onset and date of resolution
- Severity
- Seriousness
- Relationship to study treatment
- MedDRA codes and terms according to system organ class, high level term, low level term and preferred term

Severity and Seriousness of Adverse Events

Severity is a measure of intensity whereas seriousness is defined by the criteria in section 7.4 of the protocol. Severity will be assessed using the grading scales found in the National Cancer Institute CTCAE version 4.03 (June 2010) for all adverse events with an assigned CTCAE term. For those events without assigned CTCAE grades, the recommendation on page 1 of the CTCAE that converts mild, moderate and severe into CTCAE grades should be used. A copy of the CTCAE version 4.03 can be downloaded from the Cancer Therapy Evaluation Program website (<http://ctep.cancer.gov>). Any adverse event which changes CTCAE grade over the course of a given episode will have each change of grade recorded on the adverse event eCRF. All adverse events regardless of CTCAE grade will also be evaluated for seriousness.

Causality of Adverse Events

The causal relationship between the study treatment and each AE will be assessed as follows:

Unrelated: No evidence of any causal relationship

- Unlikely: There is little evidence to suggest there is a causal relationship (e.g. event did not occur within a reasonable time after administration of the trial medication). There is another reasonable explanation for the event (e.g. the patient's clinical condition, other concomitant treatment).
- Possible: There is some evidence to suggest a causal relationship (e.g. because the event occurs within a reasonable time after administration of the trial medication). However, the influence of other factors may have contributed to the event (e.g. the patient's clinical condition, other concomitant treatments).
- Probable: There is evidence to suggest a causal relationship and the influence of other factors is unlikely.
- Definite: There is clear evidence to suggest a causal relationship and other possible contributing factors can be ruled out.

Abnormal Laboratory Test Results

All clinically important abnormal laboratory test results occurring during the study will be recorded as adverse events. The clinically important abnormal laboratory tests will be repeated at appropriate intervals until they return either to baseline or to a level deemed acceptable by the investigator and the clinical monitor, or until a diagnosis that explains them is made.

Serious Adverse Event (SAE) - is defined as any event that:

- Results in death;
- Is life-threatening*;
- Requires hospitalisation or prolongation of existing inpatient's hospitalisation**;
- Results in persistent or significant disability or incapacity;
- Is a congenital abnormality or birth defect;
- Is another important medical event (that may not result in death, not be life threatening, or not require hospitalization may be considered a serious adverse event when, based upon appropriate medical judgment, the event may jeopardize the subject and may require medical or surgical intervention to prevent one of the outcomes listed above.

N.B. In addition to the above criteria, adverse events meeting either of the below criteria, although not serious per ICH definition, are reportable to Merck in the same timeframe as SAEs to meet certain local requirements. Therefore, these events are considered serious by Merck for collection purposes:

- A new cancer (that is not a condition of the study);
- Is associated with an overdose (whether accidental or intentional)

* “Life-threatening” in the definition of “serious” refers to an event in which the subject was at risk of death at the time of the event; it does not refer to an event which hypothetically might have caused death if it were more severe.

** “Hospitalisation” means any unexpected admission to a hospital department. It does not usually apply to scheduled admissions that were planned before study inclusion or visits to casualty (without admission).

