6.5 Safety Analysis

The safety data which include adverse events (AEs) and serious adverse events (SAEs) will be tabulated for the two cohorts. AEs and SAEs will be summarised by description, frequency, outcome, severity, seriousness and relationship to study treatment. Additionally, SAEs will also be summarised by SAE reason. Serious Adverse Reaction (SAR), Suspected Unexpected Serious Adverse Reaction (SUSAR) and other safety variables (e.g. pregnancy and lactation) and their frequencies, if any, will also be reported.

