[‡]Proportion change in the sum of the diameters for all target lesions at that follow-up time (or progression if prior to that follow-up time) compared to baseline

Table 5. EORTC QLQ-C30 scores

A. Cohort 1

Scales	Baseline		Month 3		Discon		p-value
	Mean Median	StDev Range	Mean Median	StDev Range	Mean Median	StDev Range	
GHS							
Physical functioning							
Role functioning							
Emotional functioning							
Cognitive functioning							
Social functioning							
Fatigue							
Nausea and vomiting							
Pain							
Dyspnea							
Insomnia							
Appetite loss							
Constipation							
Diarrhea							
Financial difficulties							

B. Cohort 2

Scales	Baseline		Month 3		Discon		p-value
	Mean Median	StDev Range	Mean Median	StDev Range	Mean Median	StDev Range	
GHS							
Physical functioning							
Role functioning							
Emotional functioning							
Cognitive functioning							
Social functioning							
Fatigue							
Nausea and vomiting							
Pain							
Dyspnea							
Insomnia							
Appetite loss							
Constipation							
Diarrhea							
Financial difficulties							

Table 6. Summary of Adverse Events (AEs)*

	Cohort 1		Cohort 2	
	No. of Events	No. of Subjects [†]	No. of Events	No. of Subjects [†]
Total Number of AEs	##	##	##	##
Severity				
Grade 1	## (##.##%)	##	## (##.##%)	##
Grade 2				
Grade 3				
Grade 4				
Grade 5				
Missing				
Relation to study medication				
Definitely				
Probably				
Possibly				
Unlikely				
Not related				
Not assessable				
Missing				
AE expectedness				
Expected				
Unexpected				
Missing				
AE classification				
Not serious				
Serious				

* Data are presented as frequency (percentage) for categorical variables

[†] A patient may have more than one AEs.

Table 7. Severity of AEs*

A. Cohort 1

	Grade					Total
	1	2	3	4	5	
MedDRA 1						
MedDRA 2						
MedDRA 3						
MedDRA 4						
MedDRA 5						
Total†						

B. Cohort 2

	Grade					Total
	1	2	3	4	5	
MedDRA 1						
MedDRA 2						
MedDRA 3						
MedDRA 4						
MedDRA 5						
Total†						

*Data are presented as number of AEs (number of patients having AEs); A patient may have more than one AE in any category and a patient is only shown once in each category, but may have AEs in more than one category.

†Each patient is counted only once in the total for the number of patients

Table 8. Relationship of AEs with study medication*

A. Cohort 1

	Relationship with study medication	
	Possible/ Probable/ Definite	Unassessable/ Unrelated/ Unlikely
MedDRA 1		

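### The AE tables print percentages of events, not of treated patients by worst grade, and do not say how an episode that changes grade is counted

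*SAP*

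**What the plan says.** SAP 5.2 lists two secondary endpoints: the incidence of adverse events up to 8 weeks after the last dose, and the same in PS2 patients. SAP 6.4 adds only that incidence will be measured.

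On recording, SAP 5.3 and protocol 7.2.1 agree. The rule applies to "Any adverse event which changes CTCAE grade over the course of a given episode", and such an event "will have each change of grade recorded on the adverse event eCRF".

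On tabulation, SAP 6.5 states that "AEs and SAEs will be summarised by description, frequency, outcome, severity, seriousness and relationship to study treatment". It does not define the unit of an event or mention a worst grade.

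The shells in SAP 6.11 add the following:
- **Table 6:** each grade row has a count with a percentage under events and a bare count under subjects. The footnote says "Data are presented as frequency (percentage) for categorical variables" and names no denominator.
- **Table 7** (term by grade, number of AEs with patients in brackets): "a patient is only shown once in each category, but may have AEs in more than one category". For the total row, "Each patient is counted only once in the total for the number of patients".
- No table in 6.11 shows adverse events for PS2 patients separately.

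A suitable denominator exists in SAP 4.2: "The Safety Population is defined as all patients who received at least one dose of Pembrolizumab". Neither SAP 6.5 nor Tables 6 and 7 refer to it.

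**The concern.** Incidence is a statement about patients: how many of those treated had an event, and how many had a severe one. The Table 6 shell attaches its percentages to events, so the figure most likely to be quoted is not the endpoint. The hypothesis in SAP 2.2 is that pembrolizumab is better tolerated than conventional chemotherapy. The figure a reader would need for that, the percentage of patients with Grade 3 or higher toxicity, has no place in the tables.

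The recording rule adds a second uncertainty. The AE data will hold several grades for some episodes by design. Changes within an episode should be common, since protocol Table 2 ties restarting treatment to a return to low grade for most listed toxicities. If the SAP does not say how such an episode enters Tables 6 and 7, two programmers could follow it faithfully and report different severe shares from the same data.

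**Working it through.** The documents give no AE rate, expected severe share or number of grade changes, so there is no planned figure to reproduce. The check has three parts. All numerical inputs are assumptions except the 31 patients, which is the lower end of the sample size range in SAP 3.5. Severe means Grade 3 or higher.

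**1. Event percentage against patient incidence, with no grade change involved.** Suppose 10 of 31 patients each have one Grade 3 event and there are 300 events in all.
- Table 6, events column: 10/300 = 3.3%, if the denominator is total events (read from the column layout; no footnote says so).
- Table 6, subjects column: 10, without a percentage.
- Patient incidence: 10/31 = 32%.

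**2. Can the proportion of patients at Grade 3 or higher be recovered?** Let n3, n4 and n5 be the patients shown under Grades 3, 4 and 5, and N the number treated. Table 7 allows one patient under several grades. The number with Grade 3 or higher therefore lies anywhere between max(n3, n4, n5) and the smaller of N and n3 + n4 + n5. It is exact only when these bounds coincide, for example when only one severe grade occurs. The total row does not help, because it covers patients with any adverse event.

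**3. Effect on event percentages if each grade record were counted as an event.** Let s be the true share of severe episodes, a and b the severe and Grade 1-2 records per severe episode, and c the records per non-severe episode. Then

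share printed = s·a / [s·(a + b) + (1 − s)·c].

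With 100 episodes, 20 of them severe (s = 20%):

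| Assumed grade path | a, b, c | Share printed |
|---|---|---|
| Severe 1-3 | 1, 1, 1 | 20/120 = 16.7% |
| Severe 2-3-2 | 1, 2, 1 | 20/140 = 14.3% |
| Severe 1-2-3-2-1 | 1, 4, 1 | 20/180 = 11.1% |
| Severe single record, half of the others 1-2-1 | 1, 0, 2 | 20/180 = 11.1% |
| Severe 3-4 | 2, 0, 1 | 40/120 = 33.3% |
| Severe 2-3-4-3 | 3, 1, 1 | 60/160 = 37.5% |
| Severe 3-4-3 | 3, 0, 1 | 60/140 = 42.9% |

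In the fourth row, c = (40×1 + 40×3)/80 = 2.

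The same seven paths at other true shares:
- s = 10%: from 0.1/(0.1 + 1.8) = 5.3% to 0.3/(0.3 + 0.9) = 25.0%.
- s = 30%: from 0.3/(1.5 + 0.7) = 13.6% to 0.9/(0.9 + 0.7) = 56.3%.

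These are not hard limits. Extra records in both groups (a = 1, b = 2, c = 2) at s = 20% give 0.2/(0.6 + 1.6) = 9.1%. Tabulating each episode once at its maximum grade returns 20/100 = 20.0% whatever the path.

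**The case against.** The strongest reply is that a recording rule is not a counting rule. The text speaks of one adverse event that changes grade within an episode, and the details collected for each event include one onset date and one resolution date. That fits a single event with several grade entries. The protocol also refers eCRF completion to a separate manual, which may settle the matter. This stands: a reader might infer that one episode will be counted several times, but the documents do not say so. They only leave it open.

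A reader might also infer that severe toxicity would be diluted. Take 100 episodes with maximum Grades 1/2/3/4 of 60/25/12/3, all starting at Grade 1 and climbing one grade at a time. The true 15% would become (15 + 3)/158 = 11.4% if steps up are counted, or (18 + 3)/216 = 9.7% with steps down as well. That result depends on the assumed path. Movement between Grades 3 and 4 raises the share, so no direction can be claimed.

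It is also fair to say that patient counts are planned. Tables 6 and 7 show subjects, and under the Table 7 footnote repeat records at one grade cannot inflate the patient count for that grade. In the first example a reader would see 10 subjects beside 3.3% and could divide by 31. That works for a single grade, but not for Grade 3 or higher once patients appear under more than one grade.

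Finally, the safety analysis is descriptive and no test or stopping threshold uses the event share. This limits the consequence to how clearly and reproducibly tolerability is reported.

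**Conclusion.** The point holds as a gap in the table specification. The endpoint is incidence, yet Table 6 prints percentages only on events, and no table gives treated patients by worst grade. The proportion with Grade 3 or higher toxicity is bounded by the planned tables but not, in general, determined by them. This conclusion does not depend on how grade changes are counted.

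Separately, the SAP does not say that an episode is tabulated once at its maximum grade. If grade records were counted as events, a true severe share of 20% could print as about 11% to 43% under the paths shown. That range rests wholly on assumed paths and on reading Table 6's denominator as total events. It does not show that repeat counting is planned or that severe toxicity will look rarer than it is. I would class this as a cheap improvement.

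**What to change.** In SAP 6.5 and the Table 6 and 7 shells:
- Define one event per episode, tabulated at its maximum CTCAE grade.
- Count each patient once at worst grade, overall and per preferred term.
- Print n (%) with the Safety Population named as denominator, and include a row for Grade 3 or higher.
- Give the same columns for patients with PS2 at baseline, because their incidence is a stated secondary endpoint.
- Keep the grade-change records for listings.

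The cost is SAP wording and slightly more table programming. No new data are needed.
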